#### 7.6 Demographic and Other Baseline Characteristics

Baseline variables to be summarized include, but are not limited to age, sex, weight, BMI, country of enrollment, HbA1c, Diabetes history, therapy history, creatinine clearance value and total insulin dose per day.

#### 7.6.1 Study Phase

For study phase a summary of subject demographics, current diabetes therapy at baseline, medical history and other baseline characteristics will be reported using appropriate summary statistics.

#### 7.6.2 Continuation Phase

For continuation phase a summary by randomization arm of subject demographics, current diabetes therapy at baseline, medical history and other baseline characteristics will be reported using appropriate summary statistics.

#### 7.7 Treatment Characteristics

Duration of Study Exposure will be measured in days starting from the time of enrollment (informed consent signed and inclusion/exclusion criteria confirmed) through and including the time of study exit.

#### 7.7.1 Study exposure for Study Phase

For study phase, the Run-In phase starts at Visit 2, and it ends at the time of randomization. It is expected that the Run-In phase will last 2 to 4 weeks.

The Study phase starts at the time of Randomization (end of Run-In phase), and it ends at Visit 11.

The study phases exposures are calculated as:

- Study phase exposure (days) = (Visit 11 date (or study exit date, if early exited) date of Randomization +1).
- Run-In phase exposure (days) = (date of Randomization (or study exit date, if early exited) Visit date) +1).
- Pre-Run-In phase exposure (days) = (Visit 2 date of Enrollment (Consent) +1).

#### 7.7.2 Study exposure for Continuation Phase

For continuation phase, the Run-In, in case of newly enrolled patients, starts at Visit 2A, and it ends at Visit 3A. It is expected that the Run-In phase will last around 10 days.

The Continuation phase starts at Visit 11, and it ends at Visit 15.

The continuation phases exposures are calculated as:

- Continuation phase exposure (days) = Visit 15 date (or study exit date, if early exited) Visit 11 date (or Visit 3A for newly enrolled patients, if any) +1).
- Run-In phase exposure (days) = Visit 12 date Visit 2A date +1.
- Pre-Run-In phase exposure (days) = Visit 2A Visit 1A +1.
- Continuation phase period 1 exposure (days) = Visit 13 date (or study exit date, if early exited) Visit 11 date (or Visit 3A for newly enrolled patients, if any) +1.
- Continuation phase period 2 exposure (days) = Visit 15 date (or study exit date, if early exited) Visit 13 date +1.

Extent of study exposures will be presented in a summary table.

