#### **Continuation Phase - Run-in 2 Phase:**

The purpose of the run-in 2 phase (3 to 10 days) is to train the newly enrolled subject's parent(s)/legal guardian(s) on the MiniMed 780G system in Manual Mode with Suspend before low activated. At the end on the continuation phase run-in 2 period, subjects will start using the 780G system in Auto Mode.

This document is electronically controlled

CIP342 LENNY Statistical Analysis Plan	Form
Revision 2.0 Page 11 of 31	Medtronic

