#### Time windows for device data metrics will be defined as follow:

Revision 2.0 Page 15 of 31

- Run-in period: from Visit 2 (excluded) to Visit 3 (excluded); •
- Study phase period 1: from Visit 3 (excluded) to Visit 7 (excluded); •
- Washout period: from Visit 7 (excluded) to Visit 8 (excluded);
- Study phase period 2: from Visit 8 (excluded) to Visit 11 (excluded); ٠
- (in case of newly enrolled subjects) Run-in 2 period: from Visit 2A (excluded) to Visit 3A ٠ (excluded);
- Continuation phase period 1: from Visit 11 (excluded) to Visit 13 (excluded); ٠
- Continuation phase period 2: from Visit 13 (excluded) on.

CGM data from the day of the visits will not be included in the device data metrics calculation to avoid any possible bias due to the change in the treatment and settings.

Time windows for safety events will be defined as follow:

- Pre-Run-in period: from ICF signature date (included) to Visit 2 (excluded)
- Run-in period: from Visit 2 (included) to Visit 3 (excluded); •
- Study phase period 1: from Visit 3 (included) to Visit 7 (included); •
- Washout period: from Visit 7 (excluded) to Visit 8 (excluded); •
- Study phase period 2: from Visit 8 (included) to Visit 11 (excluded); •
- (in case of newly enrolled subjects) Pre-Run-in 2 period: from ICF signature date/Visit 1A • (included) to Visit 2A (excluded)
- (in case of newly enrolled subjects) Run-in 2 period: from Visit 2A (included) to Visit 3A (excluded);
- Continuation phase period 1: from Visit 11 (included) to Visit 13 (excluded);
- Continuation phase period 2: from Visit 13 (included) on. •

The templates for Tables, Listings and Figures (TLFs) will be available in the TLFs document for both study and continuation phase.

It is anticipated that SAS 9.4 or later (SAS Institute Inc., Cary, NC, USA) will be used to perform all statistical analyses.

Additional exploratory analyses will be conducted as deemed appropriate and described as ad-hoc analysis in the study report.

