## 7.10 Safety Evaluation

The safety endpoints will be assessed separately for the study phase and continuation phase of the study. For study phase the events will be reported for each period (Run-In, Study phase period 1, washout period, study period 2). For the continuation phase the events will be reported for each period (Run-in 2, continuation phase period 1 and continuation phase period 2). For study and continuation phases events will be reported by both randomization arm and actual treatment received and will be presented for the Safety population.

CIP342 LENNY Statistical Analysis Plan	Form
Revision 2.0 Page 29 of 31	Medtronic

Any safety related event will be classified by study period according to the rule defined in paragraph 7.2.

The listing of these events will also be reported.

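### For children enrolled only for the continuation phase, the SAP computes run-in 2 exposure to Visit 12 instead of Visit 3A (7.7.2), and its period 1 data and safety windows open at a Visit 11 they do not have (7.2)

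*SAP*

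**What the plan says.** **Exposure (SAP 7.7.2).** The section opens with a definition: "For continuation phase, the Run-In, in case of newly enrolled patients, starts at Visit 2A, and it ends at Visit 3A". It adds: "It is expected that the Run-In phase will last around 10 days". SAP section 5 gives a similar length: "The purpose of the run-in 2 phase (3 to 10 days". The protocol synopsis allows 2 to 12 days. The exposure formula then uses a different end point: "Run-In phase exposure (days) = Visit 12 date", less the Visit 2A date, plus 1. It has no fallback for a child who leaves early. In the same list, the whole-phase and period 1 formulas start at Visit 11 with an alternative: "or Visit 3A for newly enrolled patients, if any) +1".

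**Windows (SAP 7.2).** The device-data and safety lists each have a run-in 2 line for newly enrolled subjects, and each closes it at Visit 3A, excluded. The next line of the safety list is "Continuation phase period 1: from Visit 11 (included) to Visit 13 (excluded". The device list says the same, with Visit 11 excluded. Neither offers Visit 3A as an alternative start.

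**Use of the windows (SAP 7.10).** "Any safety related event will be classified by study period according to the rule defined in paragraph 7.2". Continuation-phase events are to be reported for run-in 2, period 1 and period 2.

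**Schedule (protocol 9.1).** Continuation-only children attend Visits 1A, 2A, 3A, 12, 13, 14 and 15. Auto Mode starts at Visit 3A. They have no Visit 11.

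**The concern.** The run-in 2 formula contradicts the definition a few lines above it. By Visit 12 these children have been in Auto Mode for weeks, so the formula credits Auto Mode time to a Manual Mode run-in. The period 1 formula counts the same days again.

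The window problem is separate. Run-in 2 closes at Visit 3A, and the next window opens at a visit that does not exist for these children. A program written strictly to SAP 7.2 would assign nothing between Visit 3A and Visit 13. That is their entire period 1, not only its first weeks.

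At stake are the exposure table, the period 1 device metrics and the period to which safety events are assigned, in children aged 2 to 6 using the system under evaluation.

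**Working it through.** **Inputs (protocol 9.1, with Visit 1A as day 0)**

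- Visit 2A: day 0-3 at target; with the +5 day window, day 0 to 8.
- Visit 3A: Visit 2A + 7 ± 5 days, so 2 to 12 days after Visit 2A, or day 2 to 20.
- Visit 12: day 42 ± 5, so day 37 to 47.
- Visit 13: day 126 ± 42, so day 84 to 168.

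The SAP formulas are read as date differences plus 1.

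**Step 1. Can the SAP's figure of around 10 days be reproduced?**

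- By the definition, Visit 3A − Visit 2A + 1: 7 + 1 = 8 days at target; range 2 + 1 = 3 to 12 + 1 = 13. This agrees with around 10 days.
- By the written formula, Visit 12 − Visit 2A + 1: 42 − 0 + 1 = 43 or 42 − 3 + 1 = 40 days at target; range 37 − 8 + 1 = 30 to 47 − 0 + 1 = 48. No permitted visit dates give about 10 days.

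The overstatement is 40/8 = 5.0 to 43/8 = 5.4 times at target dates. Across windows it runs from 30/13 = 2.3 to 48/3 = 16 times.

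**Step 2. Double counting.** Days in both run-in 2 and period 1 exposure = Visit 12 − Visit 3A + 1.

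- At target: 42 − 7 + 1 = 36 (Visit 2A on day 0) or 42 − 10 + 1 = 33 (Visit 2A on day 3).
- Across windows: 37 − 20 + 1 = 18 to 47 − 2 + 1 = 46.

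Check with Visit 2A on day 0:

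- Run-in 2 as written is 43 days and period 1 is 126 − 7 + 1 = 120, a total of 163.
- The calendar span from Visit 2A to Visit 13 is 126 − 0 + 1 = 127 days. The excess is 163 − 127 = 36, which matches.
- With Visit 3A as the end point, the total is 8 + 120 = 128. Only the shared boundary day is then counted twice.

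**Step 3. Time with no period under SAP 7.2**

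- Safety (Visit 3A up to the day before Visit 13): 126 − 7 = 119 days at target, or 126 − 10 = 116 if Visit 2A is on day 3; range 84 − 20 = 64 to 168 − 2 = 166.
- Device data (strictly between the two visits): one day fewer, so 118 or 115 at target; range 63 to 165.

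**The case against.** **The intended reading is clear.** SAP 7.7.2 gives Visit 3A as the period 1 start, and a sensible programmer would carry it into 7.2. That is likely, but it shows that 7.2 omits a rule the SAP relies on elsewhere. It does not help with Visit 12, where following the formula gives a wrong number.

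**Visit 12 may be deliberate.** Protocol Table 5 labels Visit 12 as the start of continuation period 1. The same table starts Auto Mode at Visit 3A, and the protocol's visit text calls Visit 12 a follow-up. Table 5 also labels Visit 14 as the start of period 2, although randomization and the switch of device happen at Visit 13. The labels therefore cannot override the SAP's own definition.

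**The effect is conditional and peripheral.** This stands. Newly enrolled children exist only if the interim check of the HbA1c standard deviation leads to reopened enrolment.

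A reader might infer more than the documents support:

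- *That the period 1 exposure formula is also wrong.* It already has the Visit 3A alternative. The double count arises because that formula starts correctly and the run-in formula ends too late.
- *That event rates in run-in 2 would be diluted, or time per mode misreported.* SAP 7.10.1 and 7.10.2 plan rates per 100 patient-years for the study phase only, and 7.10.3 plans numbers of events. No run-in 2 rate or time-per-mode summary is planned.
- *That safety events would be lost.* The Safety Population is everyone with signed consent, and events are also listed. What is missing is a period under which to tabulate them.
- *That all the unassigned time is a child's first experience of Auto Mode.* Exclusion criterion 6 lets existing 780G users join the continuation phase.

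**Conclusion.** Both errors stand as wrong wording, and each is in its own section.

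- **SAP 7.7.2** overstates run-in 2 exposure: 40-43 days at target (30-48) against 8 (3-13). It counts 33-36 days per child twice (18-46).
- **SAP 7.2** leaves the whole of period 1 without a window for these children: about 119 safety days at target (64-166).

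The figures assume that visits fall within the protocol's windows and that enrolment is reopened. Without newly enrolled children, neither error has any effect.

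The consequences are confined to the exposure summary, the period 1 device metrics and the assignment of safety events to periods. The continuation primary endpoint (HbA1c at the end of period 2) and TIR measured in period 2 are unaffected, because the period 2 window opens at Visit 13 for everyone. The SAP does not define the baseline value used to adjust the TIR model. An effect through a period 1 baseline is possible but cannot be shown from the documents.

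The wording should be corrected before the continuation-phase outputs are programmed.

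**What to change.** 1. **SAP 7.7.2:** Run-in 2 exposure (days) = Visit 3A date (or study exit date, if the child exits early) − Visit 2A date + 1. The period 1 and whole-phase formulas need no change. The introductory sentence that starts the continuation phase at Visit 11 should carry the same Visit 3A exception.
2. **SAP 7.2, device and safety lists:** let continuation period 1 start at Visit 11 or, for newly enrolled subjects, at Visit 3A, and end at Visit 13. Keep each list's present included/excluded rule. Keep the reference to newly enrolled subjects, because the protocol also uses the label Visit 3A for the Auto Mode start of Sequence A in the study phase.

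The cost is a few lines of SAP wording and the matching derivation code. No new data are needed.

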## 7.8 Interim Analyses

#### 7.8.1 Study Phase

No Interim analysis is planned to be conducted during the LENNY study phase.

#### **7.8.2 Continuation Phase**

An interim analysis will be performed during continuation phase, when approximately 50% of subjects complete the continuation phase period 1, to evaluate sample size justification assumption on HbA1c standard deviation and re-assess sample size, if needed.

CIP342 LENNY Statistical Analysis Plan	Form
Revision 2.0 Page 20 of 31	Medtronic

## 7.9 Evaluation of Objectives

In this section detailed information about each objective is included together with calculations and derivations of outcome parameters, analysis methods, datasets analyzed (ITT and PP). For each endpoint will be reported at least summary statistics table.

# 7.9.1 Analysis of primary endpoint – study phase - between-treatment difference in TIR (70-180 mg/dL) – non inferiority test

The goal is to assess the non-inferiority in the percentage of time that the sensor glucose measurement is in the target range, 70 to 180 mg/dL (3.9-10.0 mmol/L), during each 12-week period in the Treatment 780G in Auto Mode compared to Control MiniMed 780G in Manual Mode + SBL.

The between-treatment difference will be compared using the following hypotheses:

$$\begin{aligned} H_0: \Delta TIR &\leq -7.5\% \\ H_\alpha: \Delta TIR > -7.5\%. \end{aligned}$$

Where  $\Delta TIR$  is the average of the cross-over differences in time in range in Treatment 780G in Auto Mode vs Control MiniMed 780G System + SBL ( $TIR_{AHCL} - TIR_{SBL}$ ), and the test will be at the 0.025 (one-sided) significance level.

The carryover effect will be tested using repeated measures mixed model with period, randomization sequence, and treatment as fixed effects, and subject as the random effect.

The 97.5% lower confidence limit of between-treatment difference will be calculated. If it is greater than -7.5%, the non-inferiority will be concluded.

If the p value of the coefficient for randomization sequence is ≤0.1 (there is a carryover effect), data from period 1 will be used for analysis only. The 97.5% lower confidence limit of between-treatment difference at period 1 will be calculated. If it is greater than -7.5%, the non-inferiority will be concluded.

Descriptive summary statistics of the primary endpoint will be presented stratified by treatment. In addition, descriptive summary statistics of the primary endpoint will be presented stratified by country.

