14.5.3 Analysis of Secondary Endpoints – Study Phase and Continuation Phase

CIP342 Clinical Inv			
D00674412	Version E	Page 76 of 96	Mecttronic

A fixed-sequence testing method will be applied to address the multiple comparison. If the primary endpoint analysis is significant, the procedure tests hierarchically the ordered hypotheses in sequence as the order in 4.2.2., at level a=0.025 (one-sided) until one of the hypotheses is non-rejected.

Analysis on each secondary endpoint will be performed using the same methodology in primary endpoint on the ITT population.

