#### 7.5 Adjustments for Multiple Comparisons

Study endpoints will be tested with the use of a hierarchical gatekeeping procedure to control the type I error. The primary endpoints will be tested first and, if passing the significance testing, other endpoints will be tested in order.

CIP342 LENNY Statistical Analysis Plan	Form
Revision 2.0 Page 17 of 31	Medtronic

If a non-significant result (hypothesis not rejected) is encountered, formal statistical hypothesis testing will be terminated, and analysis of any subsequent endpoints (lower in hierarchy) will be considered as exploratory.

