#### Pass/Fail Criteria:

The study pass/fail criteria are based on statistical hypothesis of the primary endpoint. The study will be considered as success when the evaluation criteria meet the predefined threshold on the ITT set.

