# 7.9.3.1 Between treatment difference in HbA1c – non inferiority test endpoints

The between-treatment difference in mean HbA1c at the end of each 12-week period will be assessed similarly to primary endpoint analysis, using repeated measures mixed model with period, randomization sequence, and treatment as fixed effects, and subject as the random effect.

The between-treatment difference will be compared using the following hypotheses:

$$\begin{array}{l} H_0: \Delta HbA1C \geq 0.4\% \\ H_\alpha: \Delta HbA1C < 0.4\%. \end{array}$$

Where  $\Delta HbA1c$  is the average of the cross-over differences in HbA1c at the end of 12-week period in Treatment 780G in Auto Mode vs HbA1c at the end of 12-week period Control MiniMed 780G System + SBL ( $HbA1C_{AHCL} - HbA1C_{SBL}$ ), and the test will be against at the 0.025 (one-sided) significance level.

CIP342 LENNY Statistical Analysis Plan	Form
Revision 2.0 Page 22 of 31	Mecttronic

The 97.5% upper confidence limit of between-treatment difference will be calculated. If it is lower than 0.4%, the non-inferiority will be concluded.

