# 7.9.3.2 Between treatment difference in TIR (70-180 mg/dL) – superiority test

The between-treatment difference in the percentage of time that the sensor glucose measurement is in the target range, 70 to 180 mg/dL (3.9-10.0 mmol/L), during each 12-week period in the Treatment 780G in Auto Mode compared to Control MiniMed 780G in Manual Mode + SBL will be assessed for superiority using repeated measures mixed model with period, randomization sequence, and treatment as fixed effects, and subject as the random effect.

The between-treatment difference will be compared using the following hypotheses:

$$H_0: \Delta TIR \le 0\%$$
  
$$H_{\alpha}: \Delta TIR > 0\%.$$

the test will be against at the 0.025 (one-sided) significance level.

The 97.5% lower confidence limit of between-treatment difference will be calculated. If it is greater than 0%, the superiority will be concluded.

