#### 7.9.3.3 Between treatment difference in HbA1c – superiority test

The between-treatment difference in mean HbA1c at the end of each 12-week period will be assessed for superiority using repeated measures mixed model with period, randomization sequence, and treatment as fixed effects, and subject as the random effect.

The between-treatment difference will be compared using the following hypotheses:

$$\begin{split} H_0: \Delta H b A 1 C &\geq 0\% \\ H_\alpha: \Delta H b A 1 C &< 0\%. \end{split}$$

the test will be against at the 0.025 (one-sided) significance level.

The 97.5% upper confidence limit of between-treatment difference will be calculated. If it is lower than 0%, the superiority will be concluded.

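### Switching the study-phase primary analysis to period 1 when the sequence test gives p ≤ 0.1 raises the one-sided level from 0.025 to about 0.035–0.047 when there is no carryover

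*SAP*

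**What the plan says.** SAP 7.9.1 tests whether Auto Mode loses less than 7.5 percentage points of TIR against Manual Mode with suspend before low, "and the test will be at the 0.025 (one-sided) significance level". The model has period, sequence and treatment as fixed effects and subject as random. The sequence coefficient doubles as a carryover test. If its p value is at most 0.1 (the plan's reading being that "there is a carryover effect), data from period 1 will be used for analysis only"), a 97.5% lower limit from period 1 alone is compared with -7.5%. Protocol 14.5.1 has the same rule. Neither section changes the level in the period-1 branch.

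The result decides the trial. SAP 7.9.1, under Pass/Fail Criteria, says: "The study will be considered as success when the evaluation criteria meet the predefined threshold on the ITT set". Protocol 14.5.1 differs here and asks for success in both the ITT and the per-protocol (PP) sets. The same test opens the hierarchy in SAP 7.5: "Study endpoints will be tested with the use of a hierarchical gatekeeping procedure to control the type I error".

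On the study-phase secondary endpoints, Protocol 14.5.3 says: "Analysis on each secondary endpoint will be performed using the same methodology in primary endpoint on the ITT population". SAP 7.9.3.1 says HbA1c non-inferiority is assessed "similarly to primary endpoint analysis, using repeated measures mixed model with period, randomization sequence, and treatment as fixed effects". SAP 7.9.3.2 and 7.9.3.3 give the two-period model and one decision rule each, with no switch: for TIR, "If it is greater than 0%, the superiority will be concluded"; for HbA1c, "If it is lower than 0%, the superiority will be concluded".

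**The concern.** In a two-period, two-sequence crossover, the sequence contrast compares the children's two-period totals between randomized groups. It cannot separate carryover from a chance difference between the groups. When it is large by chance, the period-1 comparison, which is between the same groups and uses half of the same data, tends to be off as well. The plan turns to the period-1 comparison precisely then and tests it as if it had been chosen in advance.

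Two things rest on the stated 0.025: the declaration of study success and the first gate of the hierarchy. If the rule does not hold that level, neither has the error control the plan states.

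The scope of the rule is a second problem. Read literally, after a switch the SAP would test TIR non-inferiority on period 1 only and TIR superiority on both periods, on the same endpoint in the same hierarchy.

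**Working it through.** **Inputs from the documents.** One-sided level 0.025 and margin -7.5 (SAP 7.9.1). Switch at p ≤ 0.1 (SAP 7.9.1), two-sided by the convention in SAP 7.2, so |Z| ≥ 1.645. 1:1 allocation (Protocol 9.4.1). About 72 completers (Protocol 14.6.1), so 36 per sequence, or 40 if all of about 80 randomized children are used.

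**Assumption.** The available text gives no within-child correlation ρ between the two period values of TIR, so ρ is varied.

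**The plan's own figure.** One analysis fixed in advance, with a 97.5% limit, has level 1 - Φ(1.96) = 0.025. This holds for the crossover analysis alone and for the period-1 analysis alone.

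**The rule as written, no carryover, true difference -7.5.** Let Y1 and Y2 be a child's two period values, each with variance σ².

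- Sequence test, on totals: Var(Y1 + Y2) = 2σ²(1 + ρ).
- Crossover test, on differences: Cov(Y1 + Y2, Y1 - Y2) = 0, so it is independent of the sequence test. When the switch does not fire, the level is exactly 0.025.
- Period-1 test: Cov(Y1 + Y2, Y1) = σ²(1 + ρ), so its correlation with the sequence test is (1 + ρ)/√(2(1 + ρ)) = √((1 + ρ)/2).

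Overall level = 0.9 × 0.025 + P(|Z_seq| ≥ 1.645 and Z_P1 > 1.96) = 0.0225 + the joint probability, from the bivariate normal:

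| ρ | Correlation | Joint probability | Error given a switch (joint ÷ 0.1) | Overall level |
|---|---|---|---|---|
| 0 | 0.707 | 0.0125 | 12.5% | 0.035 |
| 0.2 | 0.775 | 0.0148 | 14.8% | 0.037 |
| 0.5 | 0.866 | 0.0185 | 18.5% | 0.041 |
| 0.8 | 0.949 | 0.0229 | 22.9% | 0.045 |
| 0.9 | 0.975 | 0.0244 | 24.4% | 0.047 |

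The limit at ρ = 1 is 0.0225 + 0.025 = 0.0475.

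**Simulation check.** With t tests, 200,000 trials per setting and 36 per sequence, the level is 0.035, 0.041 and 0.047 at ρ = 0, 0.5 and 0.9. The switch fires in 9.9% to 10.1% of trials, and the crossover analysis alone gives 0.025 throughout. With 40 per sequence the levels agree to within about 0.001. The SD, the margin and a common period effect do not matter.

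**If carryover is real.** Assume SD 10, ρ = 0.5, 36 per sequence, and a carryover λ (TIR points) from Auto Mode into the following Manual Mode period. The crossover estimate is biased by -λ/2. Its standard error is √(2 × 25/36) = 1.18; that of the sequence contrast is √(2 × 300/36) = 4.08. For λ = -3, for example, P(switch) = Φ(-1.645 + 3/4.08) + Φ(-1.645 - 3/4.08) = 0.19. Simulated levels:

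| λ | P(switch) | Level, no switch | Level, current rule |
|---|---|---|---|
| -1 | 0.11 | 0.061 | 0.069 |
| -3 | 0.19 | 0.24 | 0.20 |
| -5 | 0.33 | 0.55 | 0.37 |
| +3 | 0.19 | 0.0006 | 0.025 |

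**The case against.** **The protocol asks for success in both ITT and PP.** That lowers the chance of a false success. If the switch is applied separately in each set and PP exclusions are at random (an assumption; no PP fraction is given), the joint level for ρ from 0 to 0.9 is roughly 0.023 to 0.032 with 32 of 36 per sequence in PP, and 0.020 to 0.028 with 29. So under the protocol's rule, false success may be close to 0.025. This stands as a qualification. It does not repair the ITT test, which the SAP uses alone for success.

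**Deleting the switch gives 0.025 only without carryover.** True. At a carryover of -3 or -5 points, the current rule has the lower error. But it restores 0.025 at none of the three negative values, is worse than no switch at -1, and misses a 5-point carryover in about two trials out of three.

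**A narrower repair exists.** Testing the period-1 branch at a one-sided level of about 0.0025 to 0.0034 (ρ from 0.9 to 0) would restore 0.025 with no carryover. It would cost power in that branch, the exact level depends on an unknown ρ, and a chance imbalance would still be read as carryover.

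**Late change.** Replacing a prespecified rule in an open-label trial carries its own credibility risk. This is fair, and calls for documented timing.

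**Scope.** SAP 7.9.3.1 can be read as carrying the switch over, so it is ambiguous; only 7.9.3.2 and 7.9.3.3 are silent. Protocol and SAP still need to be reconciled.

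**Conclusion.** The concern holds. With no carryover, the ITT primary test has a one-sided level of 0.035 to 0.047 for ρ from 0 to 0.9, against a stated 0.025; at ρ = 0.5 it is about 1.6 times the stated level (0.041/0.025). All of the excess comes from the 10% of trials that switch. Only ρ is assumed, and every value from 0 upward gives inflation. Nothing in either document allows for the selection, and the hierarchy in SAP 7.5 governs only the order of the endpoints.

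Power is a lesser matter. At ρ = 0.5 and a true difference of 0, always using the crossover model against the current rule gives 100% against 97% (SD 8.7), 99.9% against 95% (SD 12) and 99% against 94% (SD 15). The defect is the level.

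If Protocol 14.5.3 governs the secondary endpoints, the TIR superiority test has the same inflation; if SAP 7.9.3.2 governs, it has none.

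**What to change.** Remove the p ≤ 0.1 switch from Protocol 14.5.1 and SAP 7.9.1. Base the primary conclusion always on the two-period mixed model already specified. Report the sequence term and the period-1 estimate with its confidence interval as sensitivity analyses that do not decide success. State in Protocol 14.5.3 and SAP 7.9.3 that no switch applies to the study-phase secondary endpoints. While amending, reconcile the two success rules (ITT and PP in the protocol, ITT alone in the SAP).

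No new data are needed. The change takes a protocol amendment, with ethics and where applicable regulatory approval (Protocol 15.1 and 16.7), and an SAP revision. SAP 2.0 is dated July 2024 and the trial is open-label, so the record should say whether study-phase results were known when the change was made. The statistical price is that protection against carryover then rests on the 2-week Manual Mode washout and on the sensitivity analyses.
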